### 6.3. Losartan dosing

Participants will have their dose increased by the study team based on blood pressure response at monthly clinic visits to a max of 1.4mg/kg/day or 100mg/day. Dosing will be rounded to the closest 25 mg tablet. The study coordinator and PI will review the mean BP obtained by aneroid technique during the clinic visit and compared to either the 75th or 95th percentile normative data for systolic and diastolic BP by age, height, and gender. A dose can be increased for either a systolic or diastolic BP that is greater than the randomized target BP goal). Participants that miss a dose should not take an extra dose, rather the participant should resume their usual schedule. Losartan should be stored at room temperature, kept in a tightly closed container, and protected from light.

## 7. Safety Reporting and Adverse Events

All patients will have standard of care monthly clinic visits while on losartan. Side effects and adverse events will be recorded by study coordinator at each clinic visit. Participants will have monthly complete metabolic profiles for monitoring of potassium, liver function tests. Participants will be asked about symptoms of hypotension.

**Hyperkalemia:** Participants will have potassium monitored monthly. Potassium > 6 mEq/L will be repeated and if abnormal, the dose of losartan will be decreased. If participants are still >95th percentile blood pressure when hyperkalemia, a diuretic will be added as standard of care.

**Liver function tests:** Participants baseline AST and ALT will be recorded and compared to monthly AST and ALT levels. If AST/ALT is greater than three times the upper limit of normal, losartan will be stopped

**Symptomatic hypotension:** Participants will be asked about symptoms of hypotension prior to enrollment and at each visit including feeling lightheaded or dizzy. Participants will be asked to call the study PI to notify them of symptoms and take a blood pressure at home.

**Allergic reaction:** Participants will be asked to call the study PI if they develop swelling of the face, lips, throat, and/or tongue. Participants will be asked to describe any new rashes.

**Musculoskeletal:** Participants will be asked to describe any muscle pain, muscle tenderness, or dark urine.

Additional AEs will be documented based on participant interview and voluntary disclosure of additional toxicities. AEs will be scored using the Common Toxicity Criteria for Adverse Events 4.0.

[http://evs.nci.nih.gov/ftp1/CTCAE/CTCAE\\_4.03\\_2010-06-14\\_QuickReference\\_5x7.pdf](http://evs.nci.nih.gov/ftp1/CTCAE/CTCAE_4.03_2010-06-14_QuickReference_5x7.pdf)

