### 1.1.b Secondary Objectives

Objective 1: To determine the acceptability of enrollment and retention in a randomized feasibility trial of losartan

Objective 2: To determine the safety of losartan at two different dosing strategies

Objective 3: To complete the necessary preparations for a definitive phase III trial including preparing a manual of operations, case report forms, and sample size calculations

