##### 4.3. ABPM INTERPRETATION

To be considered an acceptable procedure, the following readings must be recorded: 1) A minimum of 1 reading per hour including during sleep and 2) total of 40 readings during the period.

Values outside the following range will be discarded

- 1) SBP 60-220 mm Hg

- 2) DBP 35-120 mm Hg
- 3) Heart rate: 40-180 BPM
- 4) Pulse pressure 40-120 mm Hg

The following calculations will be recorded

- 1) Mean Ambulatory SBP and DBP for the entire 24 hour period, awake period, and sleep period
- 2) Dipping will be calculated as ((Mean Awake BP- Mean Sleep BP)/Mean Awake BP) x 100. Normal Dipping will be defined as >10% dipping. Reverse Dipping will be defined as mean sleep BP that is higher than mean Awake BP.
- 3) BP Load is the percentage of systolic and diastolic BP readings above the 95th percentile for the 24 hour, awake, and sleep periods as defined by the 2014 Statement from the American Heart Association- Update: Ambulatory Blood Pressure Monitoring in Children and Adolescents.
- 4) BP index will be calculated as the mean BP/normative data for 95th BP for the 24 hour, awake, and sleep periods.

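### Hypotension is ascertained only through symptoms, by staff who know the BP target; no low-BP summary of the clinic or ambulatory readings is planned, and discarded ABPM readings are not counted

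*Combined protocol and SAP*

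**What the plan says.** Section 1.1.b lists as a secondary objective: "To determine the safety of losartan at two different dosing strategies". The arms differ in the clinic BP target, below the 75th or below the 95th percentile (sections 2.2 and 6.2).

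Section 7 covers hypotension by symptoms: "Participants will be asked about symptoms of hypotension prior to enrollment and at each visit including feeling lightheaded or dizzy". It continues: "Participants will be asked to call the study PI to notify them of symptoms and take a blood pressure at home". No device, threshold or recording rule is given for that home reading. The withdrawal criterion in the Data Safety and Monitoring Board text is also worded in terms of symptomatic hypotension.

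On who collects the information, section 7 states: "Side effects and adverse events will be recorded by study coordinator at each clinic visit". Section 6.3 states: "The study coordinator and PI will review the mean BP obtained by aneroid technique during the clinic visit", and the comparison is with the percentile for the assigned arm. The use given there for clinic BP is upward titration: "A dose can be increased for either a systolic or diastolic BP that is greater than the randomized target BP goal".

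ABPM is done at baseline, 3 and 6 months (sections 2.2 and 2.3). Section 4.3 records mean awake, sleep and 24-hour BP, dipping, load and index. On load: "BP Load is the percentage of systolic and diastolic BP readings above the" 95th percentile. On cleaning: "Values outside the following range will be discarded", with limits of 60-220 for SBP, 35-120 for DBP and 40-120 for pulse pressure (mm Hg), plus a heart-rate range.

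The DSMB receives percentages and 95% confidence intervals for adverse and serious adverse events. Section 9.2 mentions safety only by pointing to the DSMB.

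**The concern.** The trial is meant to inform a phase III design on whether the lower target is safe. For hypotension, that answer would rest on a count of reported symptoms. The person recording them knows which target the participant is being titrated to, and participants may know it too. Reporting can then differ between arms, in either direction, without any difference in BP.

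The trial also holds measured BP that does not depend on reporting: seated clinic readings every month and two automated 24-hour recordings after baseline. No section asks how low these readings went in each arm. Out-of-range ABPM values are dropped with no record of how many went, why, or in which arm. If low readings are lost preferentially, the retained means and any later look at low BP are shifted upwards, possibly by different amounts in the two arms.

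**Working it through.** **The plan's own numbers (section 9.1).** 200 × 0.30 = 60 eligible; 40 enrolled, about 20 per arm; with 10% dropout 40 × 0.90 = 36, about 18 per arm. These reproduce. No alpha, power, SD or hypotension rate is stated, so there is no power figure to check.

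**What a symptom count can show.** With no events in n participants, the exact upper 95% limit is 1 − 0.025^(1/n): 16.8% for n = 20 and 18.5% for n = 18. As an illustration of reporting, take a true rate of 20% in both arms and reporting of 80% in one and 50% in the other. The observed rates are 0.20 × 0.80 = 16% and 0.20 × 0.50 = 10%, a gap due to reporting alone. These rates are assumed.

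**Measured BP not assigned to safety.** Section 4.2 schedules 16 h × 3 = 48 day readings and 8 h × 2 = 16 night readings, 64 per recording. Two recordings after baseline give 2 × 64 = 128 scheduled readings, 32 of them between 10PM and 6AM. Section 4.1 gives two seated readings per visit, so 6 × 2 = 12 over the monthly visits.

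**What the filter removes.** Suppose one out-of-range component removes the whole reading. A retained reading then needs DBP ≥ 35 and SBP − DBP ≥ 40, so SBP ≥ 35 + 40 = 75. The stated SBP floor of 60 never binds. A reading of 85/50 (pulse pressure 35) also goes.

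The size was simulated with bivariate normal sleep readings and an SBP-DBP correlation of 0.6. The means and SDs are assumptions, not figures from the protocol.

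| Sleep mean | SD (SBP/DBP) | Removed overall | Removed, lowest tenth of SBP | Removed, rest | Mean SBP, all → kept |
|---|---|---|---|---|---|
| 115/65 | 10/8 | 11.2% | 44% | 8% | 115.0 → 116.4 |
| 115/65 | 12/10 | 16.0% | 53% | 12% | 115.0 → 117.1 |
| 105/58 | 10/8 | 20.1% | 64% | 15% | 105.0 → 107.2 |
| 105/58 | 12/10 | 25.3% | 73% | 20% | 105.0 → 108.3 |
| 100/52 | 10/8 | 18.3% | 66% | 13% | 100.0 → 102.2 |
| 100/52 | 12/10 | 25.4% | 80% | 19% | 100.0 → 103.6 |
| 95/48 | 10/8 | 24.5% | 82% | 18% | 95.0 → 98.0 |
| 95/48 | 12/10 | 32.8% | 94% | 26% | 95.0 → 99.7 |

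By single limit, SBP < 60 removes at most 0.2% of readings, DBP < 35 from 0.01% to 9.7%, and pulse pressure < 40 from 11.2% to 24.3%. A hand check of the first row: the pulse-pressure variance is 100 + 64 − 2 × 0.6 × 10 × 8 = 68, SD 8.25; P(pulse pressure < 40) = Φ((40 − 50)/8.25) = 11%, as simulated.

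Loss among the lowest tenth rises steadily as mean BP falls. Overall loss does not rise at every step (20.1% at 105/58, 18.3% at 100/52, both with SD 10/8), because it also depends on the assumed mean pulse pressure (47 and 48 mm Hg there). A difference in loss between arms is therefore possible but not certain.

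**The case against.** The strongest reply is that this is a 40-person feasibility trial and no planned analysis becomes wrong. Adverse events are graded by CTCAE 4.0, an independent DSMB looks for excess serious events by group, clinic BP is measured by staff every month, and range limits are a normal artefact filter. All of that stands. It makes this an improvement to the safety answer, not the correction of an error. It does not supply a low-BP summary or a count of what was filtered out.

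Several stronger readings are tempting and are not supported:

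- A reader might infer that section 4.3 summarises only high BP. It also records mean awake and sleep BP and dipping, and section 9.1 already plans a between-arm comparison of nocturnal BP improvement. What is missing is the low tail and its use for safety.
- A reader might blame the floors of SBP 60 and DBP 35. Under the assumptions above they remove few readings, except DBP at the lowest assumed pressures. The pulse-pressure floor does most of the work.
- A reader might argue from power. For symptoms in 10% vs 30%, Fisher power is 24% with 20 per arm, against 65% for a continuous measure carrying the same 0.76 SD shift. If ABPM carries only half that shift, its power is 21%, so the advantage rests on the assumption. A lower mean BP is also the intended effect of the lower target, so detecting it is not detecting harm.
- A reader might call hypotension the main risk of the lower target, or suppose it occurs mostly at night. The documents establish neither. The Potential Risks text names hypotension in volume-depleted patients as one of several warnings.

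**Conclusion.** The point holds as a gap in how the safety objective is answered. Hypotension is ascertained by symptom questions and a symptom-prompted home BP, recorded by a coordinator who works with the arm's target. That the trial is open is inferred from target-based titration and the absence of any blinding provision. Clinic BP and ABPM are collected but not used for safety, and filtered readings are not counted.

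The filter could remove 44% to 94% of the lowest tenth of sleep SBP readings, against 8% to 26% of the rest, and raise mean sleep SBP by 1.4 to 4.7 mm Hg. Those figures rest on the assumed BP distributions and on one bad component deleting the whole reading. The floor at SBP 75 needs only the second assumption. Whether losses would differ by arm cannot be determined from the documents; an uncounted filter would leave that unknown at the end of the trial as well.

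**What to change.** Add to section 9.2, for the safety objective in 1.1.b, a prespecified descriptive table by arm at 0, 3 and 6 months, with arm differences and 95% confidence intervals and no hypothesis test. It should give:

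- the lowest awake and sleep SBP and DBP;
- the share of readings below a low-BP limit fixed before analysis;
- the number of readings dropped by each filter separately (SBP, DBP, pulse pressure).

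Show the low-BP figures both before and after filtering, and state in section 4.3 whether one out-of-range component removes the whole reading. Present monthly clinic BP in the same way.

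The cost is one table from data already collected, provided the unfiltered ABPM files are kept. No visit, procedure or care rule changes, and the low-BP limit is for reporting only. The downsides are that the limit must be chosen in advance and that some low readings will be artefact, which is why both sets of counts are needed.

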### Reporting of Events

Serious safety events will be reported to the DSMB and IRB which will make recommendations to the study PI. Unexpected SAE will be reported to the DSMB and IRB within 7 calendar days if fatal or life-threatening, and within 15 calendar days if not. All SAE will be provided to the DSMB quarterly. All AE (serious and non-serious) will be reported to the DSMB every six months.

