#### 2.3.b Follow-up

1. Monthly evaluations (6 months total from randomization)
  - a. Participants will have monthly clinic visits
  - b. Obtain vital signs
  - c. Obtain standard of care labs: including CBC, CMP
  - d. Complete assessment of potential side effects of losartan
  - e. Complete assessment of adherence
2. Three months from randomization
  - a. Obtain overnight urine specimens for urine biomarkers including standard evaluation of microalbumin/creatinine ratio and experimental evaluation of biomarkers
  - b. Obtain cystatin C
  - c. Buccal Cell Collection
  - d. Repeat 24 hour ABPM
3. Six months from randomization
  - a. Obtain overnight urine specimens for urine biomarkers including standard evaluation of microalbumin/creatinine ratio and experimental evaluation of biomarkers
  - b. Obtain cystatin C
  - c. Buccal Cell collection
  - d. Repeat 24 hour ABPM

Table XX: Baseline and monthly evaluations

Test	Entry	1 mo	2 mo	3 mo	4 mo	5 mo	6 mo
Vital Signs, Hx and PE	X	X	X	X	X	X	X
CBC with diff	X	X	X	X	X	X	X
CMP	X	X	X	X	X	X	X
Adherence Measures		X	X	X	X	X	X
Ferritin	X			X			X
Cystatin C	X			X			X
Uric Acid	X			X			X
Urine Microalbumin/Creatinine	X			X			X
Overnight Urine Collection	X			X			X
24 hr ABPM	X			X			X
Urine and blood biomarkers	X			X			X
Pregnancy Test	X	X	X	X	X	X	X
Enrollment Survey	X						
Buccal Cell collection	X			X			X

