### Expected Adverse Events in Children with Sickle Cell Disease

- Acute chest syndrome
- Aplastic crisis
- Anemia
- Bacteremia
- Cholelithiasis, cholecystitis, biliary tract obstruction
- Dehydration
- Fever
- Gastroenteritis
- Headache
- Hematuria
- Hyposthenuira
- Hyperbilirubinemia
- Leukocytosis
- Nocturia
- Obstructive sleep apnea
- Osteomeylitis
- Otitis media
- Pain
- Pharyngitis
- Pneumonia
- Priapism
- Splenic sequestration
- Upper respiratory tract infections
- Urinary tract infections
- Tachycardia

Tachypnea  
Thrombocytosis

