#### Potential Risks

Losartan: This medication is FDA approved to treat hypertension. The FDA warnings include fetal toxicity (Pregnancy Category D) and Hypotension-Volume Depleted Patients. Female participants will have monthly pregnancy tests performed and educated to stop Losartan immediately if pregnant. Participants will be excluded if they are on a medication that leads to volume depletion (diuretics) and educated about volume depletion. Precautions for losartan include 1)hypersensitivity (Angioedema)- participants will be educated on angioedema and immediately removed for life threatening events, 2) impaired hepatic function- participants will have monthly liver function tests, 3) impaired renal function in patients whose renal function depends on the renin-angiotensin-aldosterone system (i.e. CHF), 4) electrolyte imbalance- participants will have monthly electrolyte levels.

Alternative treatments: The alternative to participation in this trial is to have usual care, with an anti-hypertensive medication.

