## Data Safety and Monitoring Board

We will identify investigators (at least 4 members to include a pediatric hypertension expert, sickle cell expert, patient representative, and biostatistician) to participate in an independent DSMB to monitor study safety and minimize research associated risk. Incidence of adverse events during the 6 month period will be analyzed during all mentoring meetings and independently by the DSMB. The percentage and 95% confidence intervals for serious adverse events and adverse events will be recorded and sent to DSMB every 3 months. The DSMB will evaluate excessive SAEs overall or in any one group and consider either: 1) reducing the dose of losartan or 2) closing the study and offering an alternative hypertensive medication. Patients will be withdrawn from the trial if they experience angioedema, recurrent symptomatic hypotension despite dose reduction, hyperkalemia, or recurrent symptomatic hypoglycemia.

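### A fatal or life-threatening SAE that counts as expected has no guaranteed reporting deadline sooner than the quarterly DSMB listing, and no deadline at all to the IRB

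*Combined protocol and SAP*

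**What the plan says.** Four parts of section 7 and one line of section 2.3.b bear on this.

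- **Reporting of Events** opens with a general statement: "Serious safety events will be reported to the DSMB and IRB which will make recommendations to the study PI". It gives no time limit. The expedited rule follows: "Unexpected SAE will be reported to the DSMB and IRB within 7 calendar days if fatal or life-threatening", "and within 15 calendar days if not". The next sentence covers the rest: "All SAE will be provided to the DSMB quarterly". That listing goes to the DSMB; the IRB is not named in it.
- **The list of expected events**, headed "Expected Adverse Events in Children with Sickle Cell Disease", has 27 entries. They run from headache and otitis media to acute chest syndrome, aplastic crisis, bacteremia, pneumonia and splenic sequestration. Dehydration is also on it. No entry is qualified by grade, outcome or relation to losartan.
- **Serious adverse event (SAE)** counts death and life-threatening events as serious without exception. It makes an exception for expected events only under the hospitalization criterion.
- **Data Safety and Monitoring Board** adds a second periodic route: "The percentage and 95% confidence intervals for serious adverse events and adverse events will be recorded and sent to DSMB every 3 months". It also gives the board the option of considering a lower losartan dose or closure if SAEs are excessive overall or in one arm.
- **Section 2.3.b** fixes each participant's follow-up: "Monthly evaluations (6 months total from randomization").

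**The concern.** The trigger for fast reporting is unexpectedness alone. Severity only decides between 7 and 15 days once an event is already unexpected. In sickle cell disease several conditions that can kill are also familiar, and the list names them. Read plainly, a death from acute chest syndrome is an SAE, but it is not an unexpected one, so neither clock starts.

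This matters because the DSMB's task is comparative. One death from a listed condition may mean nothing; two in the intensive arm might. Whether a familiar event is occurring too often in one arm is a question for the board, and it cannot be answered if the events arrive months late. With 40 participants, a very small number of deaths could decide whether the trial continues. Safety of the two dosing strategies is a stated objective (section 1.1.b, Objective 2), and the introduction gives the absence of prospective antihypertensive trials in adolescents with sickle cell disease as the reason for running a feasibility trial first.

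**Working it through.** The plan gives no figure for reporting delay, so there is nothing to reproduce. The check has two parts.

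**1. Which events have a timed route.** Combining the SAE definition, the expected list and the reporting rules:

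| Event | SAE? | Timed route to DSMB | Timed route to IRB |
|---|---|---|---|
| Fatal or life-threatening, unexpected | Yes | 7 days | 7 days |
| Other SAE, unexpected | Yes | 15 days | 15 days |
| Fatal or life-threatening, on the expected list | Yes | Quarterly | None stated |
| Hospitalization for a listed event, no other criterion met | No | Only as an AE (six-monthly report; 3-monthly summary percentages) | None stated |

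The third row is the gap. The untimed opening sentence of Reporting of Events applies to it but sets no date.

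**2. How long the wait can be.** Inputs: listing interval 3 months (Reporting of Events; the same interval in the DSMB section); follow-up 6 months (section 2.3.b); expedited limit 7 days (Reporting of Events). One quarter is taken as 365.25 / 4 = 91.3 days and six months as 365.25 / 2 = 182.6 days.

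- Longest wait as a share of follow-up: 3 / 6 = 0.50.
- Longest wait against the expedited limit: 91.3 / 7 = 13.0 times as long.
- Average wait, assuming that events fall evenly within a quarter: 91.3 / 2 = 45.7 days, and 45.7 / 182.6 = 0.25 of follow-up.
- Share of such events waiting longer than 7 days, same assumption: 1 − 7 / 91.3 = 0.92.
- Longest wait if the 7-day clock applied: 7 / 182.6 = 0.038, about 4% of follow-up.

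These figures assume that the listing is sent on the last day of the quarter and includes everything up to that day. Any preparation time would add to them.

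**The case against.** **The general sentence already covers these events.** A reader might infer from the gap that a listed death reaches the DSMB only through the quarterly listing. The documents do not support that. The opening sentence of Reporting of Events sends serious safety events to the DSMB and IRB whether or not they are expected, and a diligent team could report a death the next day. What stands is narrower: no deadline is guaranteed before the quarterly listing.

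**Expectedness is not defined by the list.** No sentence says that a listed condition remains expected when it is fatal. Death is not itself an entry, and an investigator could class a fatal outcome as unexpected. The text allows this but does not require it. Since the list is the only reference for expectedness and carries no limit by outcome, prompt reporting of a death would rest on an unstated interpretation.

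**The people treating participants are not in the dark.** This is correct. Adverse events are recorded at each monthly visit (section 7), the coordinator and PI review blood pressure monthly (section 6.3), and the individual withdrawal criteria in the DSMB section do not wait for the board. It would be wrong to infer that dose decisions are made in ignorance of the event. The gap concerns the DSMB's knowledge.

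**A disease list has a purpose.** It keeps routine sickle-cell events from flooding the board. That reason is sound for fever or pain. It does not extend to deaths and life-threatening events, which should be few.

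**Conclusion.** The point holds as a gap in the reporting rule. For a fatal or life-threatening case of a listed event, the guaranteed interval to the DSMB is up to about 91 days rather than 7, half of a participant's follow-up. The average is about 46 days if events fall evenly within a quarter. To the IRB there is no stated interval. The figure of 91 days is the worst case, for an event just after a listing. The conclusion rests on reading the expected list as the reference for what is unexpected, which is the natural reading but is not stated.

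Three stronger statements should not be drawn from this:

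- **Hypotension is not exempted.** It is not on the expected list, and neither are hyperkalemia or angioedema. Serious cases of these are unexpected on the same reading and already have a clock.
- **The documents do not show that the list covers most of the serious events in this population.** They give no such figure. The introduction attributes 15–30% of sickle-cell deaths to kidney disease, and renal failure is not listed.
- **The documents do not say that there are no prior paediatric safety data.** They say only that no prospective antihypertensive trials have focused on adolescents with this disease.

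**What to change.** Reword Reporting of Events so that every fatal or life-threatening SAE goes to the DSMB and IRB within the existing 7 calendar days, whether or not it is expected. Keep the 15-day clock for other unexpected SAEs and the quarterly listing for the remainder. This changes one paragraph, needs no new procedure, and costs a few additional expedited reports in a trial of 40.

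It would be unwise to go further and judge expectedness against losartan's known risks as well. That could be read as adding those risks to the expected reference, in which case a serious but non-fatal angioedema or hyperkalemia would lose its 15-day clock.

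Two related matters need separate reconciliation, since the change above does not reach them:

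- **Dehydration.** It is listed as expected, and the SAE definition exempts expected events from the hospitalization criterion. A hospitalization for dehydration that meets no other criterion is therefore not an SAE. Yet Potential Risks states: "The FDA warnings include fetal toxicity (Pregnancy Category D) and Hypotension-Volume Depleted Patients". The list, the hospitalization exemption and this warning should be made consistent.
- **AE reporting interval.** Reporting of Events sends all AEs to the DSMB every six months, while the DSMB section sends AE percentages every 3 months. The two sections should say how these fit together.
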